11.4 SAFETY ANALYSES

11.4.1 Adverse Events

All AEs will be classified using the version of the MedDRA coding dictionary specified in the DMP.

Events will be classified as treatment-emergent if they started or increased in severity on or after the first date and time of medication dosing at Day 0 and up to study closure or withdrawal date. If an event start date is partial, then the start day, month, year or stop date will be used to determine if the event is treatment-emergent. If the classification of the AE cannot be determined from the data available, then the event will be considered treatment-emergent.

An overall summary table will be presented for AEs occurring from baseline to the end of the study in the following categories (*Table 14.3.1.1*):

- Any adverse event;
- Any TEAE;
- Any serious adverse event (SAE);
- Any severe adverse event (Common Toxicity Criteria [CTC] grade 3 or 4);
- Death

The primary safety endpoint, the rate of all TEAEs will be compared between the treatments by stratified likelihood ratio chi-square test on a 10% one-sided significance level and presented in the same table.

TEAEs will be further classified as follows:

Severe TEAEs: Severity classified as 'severe' (Common Toxicity Criteria [CTC] grade 3 or 4) or missing.

Serious TEAEs: Serious classified as 'yes' or missing.

Drug-related TEAEs: Relationship to study drug classified as 'yes' or missing.

Serious drug-related TEAEs: Both serious and drug-related, as specified above.

TEAEs leading to study drug discontinuation: Action taken classified as 'permanent discontinuation'.

TEAEs overall and in each of the above classifications will be summarised separately for the following periods (Tables 14.3.1.2.1 and 14.3.1.2.2):

- Period 1: Adverse event occurs or worsens from first dosing to Day 56
- Period 2: Adverse event occurs after Day 56

Summaries by SOC and PT will also be presented for TEAEs in the two periods (*Tables 14.3.1.3.1.1* and 14.3.1.3.1.2). Similar tables will be presented for each of the classifications of treatment-emergent events above (*Tables 14.3.1.3.2.1* and 14.3.1.3.6.2).

All AE summary tables will show the number (%) of patients having at least one event and the number of events in each treatment group and overall. Note: If a patient has multiple AEs with the same preferred term, these will be summarised once within the count for N (%) of patients, but each event will be counted within the number of reports n of each AE. Changes in severity of the same AE (if collected) will be counted only once within the number of reports n of each AE.

All adverse events (including non-treatment-emergent events) recorded on the eCRF will be listed within the data listings.

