3.1.3. Dose limiting toxicity (DLT)

A dose limiting toxicity (DLT) is defined as a grade 3 or higher adverse event as defined by the Common Terminology Criteria for Adverse Events (CTC-AE v4.0) considered by a safety review board as probably or definitely related to study treatment. The first three subjects will be enrolled first and followed up for at least 2 weeks of treatment. If more than one DLT occur of the first three treated subjects, then the enrolment of additional subjects will be stopped, otherwise the enrolment of planned subjects will be confirmed.

In addition, in case of a life threatening (grade 4) adverse reaction enrolment and treatment of ongoing subjects will be immediately discontinued.

In both cases, enrolment will only be resumed upon the decision of the sponsor if the Data Safety Monitoring Board can conclude that the causality of the event was unrelated or unlikely related to study treatment.

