3.1.4. Data Safety Monitoring Board

An independent Data Safety Monitoring Board (DSMB), with expertise and experience in the pathology, and without direct involvement in the conduct of the trial, will be set up specifically to guarantee effective protection of subjects, insure the ethical conduct of the trial, benefit/risk ratio of the trial, and to ensure the independent review of the scientific results during the trial and at the end of the trial.

The DSMB will meet first after the 3 first subjects are enrolled and treated for at least 2 weeks and then every group of 3 subjects. Besides, the DSMB may recommend the early termination of the trial at any time if an unacceptable toxicity occurs.

The DSMB has only a consultative role; it will inform the sponsor who will decide whether the DSMB recommendation will be followed. A DSMB charter must be available upon submission of the trial (initial protocol) to the respective competent authorities.

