9.3. Safety Analyses

Adverse events will be coded using the standard dictionary (MedDRA) down to the lower level term (LLT).

An overall summary table will be presented (Any adverse event, any treatment emergent adverse event (TEAE), any serious adverse event (SAE), death, any grade 3 or higher adverse events from baseline to the end of Study. This analysis will be conducted on SAF population.

Two periods will be defined for TEAE:

- Any adverse event which occurs or worsens from first dosing to Day 56;
- Any adverse event which occurs after Day 56.

Adverse events will be described by primary system organ class and preferred term. Numbers and percentage of subjects, and number of occurrence of adverse event will be presented for:

- TEAE:
- Serious TEAE;
- TEAE leading to drug discontinuation;
- TEAE of grade 3 or 4;
- TEAE for which relationship with the study drug is recorded as possible or probable.

Analysis of safety will be performed on the safety data set consisting all subjects who received at least one dose of ABX464 in the study.

Primary safety endpoint, the rate of all treatment emergent adverse experiences will be compared between the study groups by stratified likelihood ratio chi-square test on a 10% one-sided significance level.

Further assessment of safety will be based on the frequency of adverse events (with and without regard to causality) graded according to the CTC-AE Classification and also, the review of individual values for clinical laboratory data, vital signs and ECG focusing on the detection of abnormal values and PCSAs [potentially clinically significant abnormalities (PCSAs) determined upon investigator considerations].

Adverse events will be tabulated (counts and percents) by group. All adverse events will be listed and the data will be tabulated by body system/organ class. Adverse event tabulations will include all treatment emergent adverse events, which will be further classified by severity, and relationship to treatment and dose level.

Clinical laboratory parameters, vital signs, ECG will be summarized by using descriptive statistics (n, mean, SD, SEM, median, minimum and maximum). Number of subjects with at least one abnormal values will be tabulated (counts and percents) for each parameter in summary shift tables, by group and dose.

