00	xx	xx (xx.x%)	××	xx (xx.x%)	xx	xx (xx.x%)
РΥ	××	xx (xx.x%)	xx	xx (xx.x%)	xx	xx (xx.x%)
PT	xx	xx (xx.x%)	xx	xx (xx.x%)	xx	xx (xx.x%)
Etc	xx	xx (xx.x%)	xx	xx (xx.x%)	××	xx (xx.x%)

The table presents number of events (n) and number and percentage of patients (N(%)) The denominator for each percentage is the number of patients within the column

Repeat for moderate and severe intensity on a new page.

Source: Listing 16.x.x

Path\Filename

Page x/y

This layout also applies to:
Table 14.3.1.3.7.2 Treatment-Emergent Adverse Events, by Intensity and SOC and PT: Period 2 (Safety Set)

Version date: 23 August 2018

Page 54 of 93

Table 14.3.2.1.1 Summary of Haematology Parameters (Safety Set)

ddMMMyyyy

		ABX-464	Placebo	Total
	***************************************	(N=xx)	(N=xx)	(N=xx)
Haematocrit				
Baseline	N	xx	xx	xx
	Mean	xx.xx	xx.xx	xx.xx
	SD	xx.xx	xx.xx	xx.xx
	Median	xx.xx	xx.xx	xx.xx
	Minimum	xx.x	xx.x	xx.x
	Maximum	xx.x	xx.x	xx.x
Day 7				
Etc				
Etc				
purce: Listing 16.x.x				
ath\Filename				Page x/y

Version date: 23 August 2018

This layout also applies to:

Page 55 of 93

Table 14.3.2.1.2 Summary of Biochemistry Parameters (Safety Set) Table 14.3.2.1.3 Summary of Stool Results (Safety Set)

Version date: 23 August 2018

Page 56 of 93

ddMMMyyyy

ABX464-101 Table 14.3.5.1 Shift Table of Haematology Parameters (Safety Set)

ABX-464 Placebo (N≃xx) (N=xx) (N=xx) Baseline Baseline Baseline Normal Normal Normal Abnormal NCS Abnormal NCS Abnormal NCS Abnormal CS Abnormal CS Abnormal CS Haematocrit Day 7 Normal xx (xx.x%) Abnormal NCS xx (xx.x%) Abnormal CS xx (xx.x%) Day 14 Etc Etc

Version date: 23 August 2018

Page 57 of 93

CS=Clinically Significant; NCS=Non Clinically Significant

The denominator for each percentage is the number of non-missing observations within the column Baseline is defined as the last non-missing value before the first dose of study drug.

Source: Listing 16.x.x

Path\Filename

Page x/y

This layout also applies to:
Table 14.3.2.2.2 Shift Table of Biochemistry Parameters (Safety Set)
Table 14.3.2.2.3 Shift Table of Stool Results (Safety Set)
Table 14.3.4.2 Shift Table of 12-Lead Electrocardiogram (Safety Set)

ABX464-101

Table 14.3.3 Vital Signs, including Weight (Safety Set)

ddMMMyyyy

		ABX-464	Placebo	Total
		(N=xx)	(N=xx)	(N≃xx)
Systolic BP (mmHg)				
Baseline	Ŋ	xx	xx	xx
	Mean	xx.xx	xx.xx	XX.XX
	SD	xx.xx	xx.xx	XX.XX
	Median	xx.xx	XX.XX	xx.xx
	Minimum	xx.x	xx.x	xx.x
	Maximum	xx.x	xx.x	xx.x
Day 7				
Etc				

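### The severe category is capped at grade 4 in SAP 11.4.1 and in one of two places in protocol 9.3, so an event graded higher falls outside the severe counts

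*SAP*

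**What the plan says.** Severity is graded on CTC-AE version 4.0 (protocol 8.5). The cut-off for the worst events is then worded in several ways.

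- Protocol 9.3, overall summary: "any grade 3 or higher adverse events from baseline to the end of Study", with death as a separate item.
- Protocol 9.3, tables by organ class and preferred term: "TEAE of grade 3 or 4".
- SAP 11.4.1, overall summary (Table 14.3.1.1): severe means CTC grade 3 or 4, with death as its own category.
- SAP 11.4.1, classification of TEAEs: "Severe TEAEs: Severity classified as 'severe' (Common Toxicity Criteria [CTC] grade 3 or 4) or missing".
- SAP 15, shell for the by-intensity tables (14.3.1.3.7.x): a mild page, then "Repeat for moderate and severe intensity on a new page". No further category is given.
- SAP 10.1: severity changes reported under one event number are merged into one event at its worst severity for the summary tables.

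Protocol 3.1.3 uses grade for a different purpose. "A dose limiting toxicity (DLT) is defined as a grade 3 or higher adverse event", subject to a judgement of relatedness, and "If more than one DLT occur of the first three treated subjects, then the enrolment of additional subjects will be stopped". The halt sentence says that "in case of a life threatening (grade 4) adverse reaction enrolment and treatment of ongoing subjects will be immediately discontinued".

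**The concern.** Safety is the primary objective, and the severe-event tables are one of the ways the two arms will be compared. A severity rule should be open at the top. This one stops at grade 4, yet it counts a TEAE of unknown grade as severe. Including the unknown and excluding the highest is unlikely to be what anyone intended.

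The cap also means that the SAP does not deliver the overall row that protocol 9.3 describes, and that an event could qualify as a DLT under protocol 3.1.3 without being counted in the severe tables. With 20 and 10 planned subjects, one subject is a visible share of an arm.

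**Working it through.** No figure in the plan needs reproducing, so the check sets the rules side by side and follows one event through them.

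**1. The cut-offs**

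| Place | Grades covered |
|---|---|
| Protocol 3.1.3, DLT definition | 3 and above |
| Protocol 3.1.3, halt sentence | life-threatening, with grade 4 in parentheses |
| Protocol 9.3, overall summary | 3 and above; death listed separately |
| Protocol 9.3, organ class and preferred term | 3 or 4 |
| SAP 11.4.1, Table 14.3.1.1 | 3 or 4; death listed separately |
| SAP 11.4.1, severe TEAEs | 3, 4 or missing |
| SAP 15, Tables 14.3.1.3.7.x | mild, moderate, severe |

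The conflict begins inside protocol 9.3. For the severe-TEAE tables the SAP follows the capped protocol bullet. For the severe row of Table 14.3.1.1 it departs from the open-ended protocol wording.

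**2. An event recorded above grade 4.** It is neither grade 3 or 4 nor missing. Programmed literally, it is left out of:
- the severe row of Table 14.3.1.1;
- the severe rows of Tables 14.3.1.2.1 and 14.3.1.2.2;
- Tables 14.3.1.3.2.1 and 14.3.1.3.2.2.

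It also has no stated category in Tables 14.3.1.3.7.1 and 14.3.1.3.7.2.

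**3. A TEAE with no grade.** It is counted in the severe TEAE tables.

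**4. An event first recorded at grade 4 and later higher under the same number.** SAP 10.1 keeps the worst severity, so the merged event leaves the severe tables because it worsened.

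**5. Where a fatal event still appears.** Death is a seriousness criterion (protocol 8.2), so the event is in the death row and the serious row of Table 14.3.1.1, in the serious rows of Tables 14.3.1.2.x, and in Tables 14.3.1.3.3.x. If related, it is also in the drug-related and serious drug-related tables. Listing 16.2.7 shows its grade and outcome.

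**6. Size.** The tables count subjects with at least one event (SAP 11.4.1). Using the planned arm sizes, one subject is:
- ABX464: 1/20 = 5 percentage points;
- placebo: 1/10 = 10 percentage points.

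These are upper bounds. They apply only if the subject has no other event that qualifies for the same row (grade 3 or 4, or ungraded in the TEAE tables). If no event is graded above 4, the effect is zero.

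**The case against.** The strongest reply is that little can go wrong. Neither document mentions a grade 5. Death is handled as an outcome of the causal event (protocol 8.2 and 8.5), and a fatal event left at grade 3 or 4 would be counted as severe. Deaths have their own row beside the severe row, and the serious-event tables show them by arm, period and organ class. Severe events are not a named endpoint, and the primary comparison uses all TEAEs whatever their grade. SAP 15 also lets programmers adapt layouts, so a higher grade could be accommodated in the by-intensity tables.

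All of this stands, and it limits the importance of the point. It does not remove the inconsistency. The documents do not say which grade a fatal event receives, the protocol's own open-ended wording allows for more than grade 4, and freedom over layout does not change a written definition of severe.

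A reader might infer two stronger things. One is that the worst events vanish from the safety report; step 5 above shows that they do not. The other is that a fatal reaction would not halt the trial. The documents do not support that either. Protocol 8.2 defines life-threatening as being at risk of death at the time of the event, which a fatal reaction would ordinarily meet, so the halt sentence can reasonably be read to cover it. In addition, "the DSMB may recommend the early termination of the trial at any time if an unacceptable toxicity occurs", although its role is consultative, and the sponsor may suspend the study for safety (protocol 11.8).

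**Conclusion.** The point holds as an error of definition with limited reach. The severe row of Table 14.3.1.1 does not match the protocol's overall summary, protocol 9.3 disagrees with itself, and the literal rule gives a wrong severe count for any event graded above 4. The conclusion assumes that such a grade can be recorded; the eCRF is not available to confirm this. The percentages in step 6 assume that the safety set matches the planned 20 and 10. The primary test does not change.

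The protocol 3.1.3 issue is one of silence. The halt sentence and the DLT definition name different grades, the DLT rule needs more than one DLT among the first three treated subjects, and a single fatal reaction is not expressly named in either trigger. Priority is minor.

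**What to change.** - In the protocol 9.3 bullet and in both places in SAP 11.4.1, replace grade 3 or 4 with grade 3 or higher. Keep the missing-grade clause for severe TEAEs.
- State that grades above 4 are counted in the highest category of Tables 14.3.1.3.7.x.
- Ask the sponsor and DSMB to reconcile the halt sentence and the DLT definition in protocol 3.1.3, so that the handling of a fatal reaction is explicit. No clinical rule is proposed here.

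The cost is a few words in each document. No new data, table or test is needed.

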If changes in severity for the same TEAE have been reported separately but with the same adverse event (AE) number, they will be collapsed to a single AE with maximum severity for the summary tables, but listed as reported.

Classifications of medical history, concomitant medication and adverse events will be sorted alphabetically within the summary tables.

If any laboratory assessments are repeated at the same visit, the result from the repeat assessment will be used in summaries. Both values will be listed.

Data collected on the eCRF will be presented within data listings. The data listings will be sorted by treatment group, country, centre number, patient number and visit/week/day. Treatment group will be as allocated (randomised). If any patients receive the wrong treatment this will be flagged in all listings. Visits outside the visit windows will be identified within the listings.

The date format for all output presentations will be 'ddMMMyyyy'.

All statistical analysis will be performed using SAS 9.3 or higher.

P-values will be rounded to four decimal places. P-values less than 0.0001 will be reported as <0.0001 in tables.

If any of the assumptions underlying the formal statistical methods proposed are violated during the analysis of the final data, alternative statistical methods will be used and any changes documented in the statistical methods section of the CSR, including the rationale for use.

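### Period 2 of the adverse event tables counts only onsets after Day 56, so an event that worsens after Day 56 can fall in neither period or be shown as severe in Period 1

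*SAP*

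**What the plan says.** SAP 11.4.1 gives a general definition: "Events will be classified as treatment-emergent if they started or increased in severity on or after the first date and time of medication dosing". The definition runs on to study closure or withdrawal, so it does not stop at Day 56.

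The same section then divides treatment-emergent events in two:

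- "Period 1: Adverse event occurs or worsens from first dosing to Day 56"
- "Period 2: Adverse event occurs after Day 56"

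The SAP takes this split from protocol 9.3, which pairs "Any adverse event which occurs or worsens from first dosing to Day 56" with "Any adverse event which occurs after Day 56".

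Two further rules decide how a change of grade is tabulated. SAP 10.1 says of severity changes reported separately under one AE number that "they will be collapsed to a single AE with maximum severity for the summary tables, but listed as reported". SAP 11.4.1 adds: "Changes in severity of the same AE (if collected) will be counted only once within the number of reports n of each AE". Neither rule mentions periods.

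The split reaches almost all the detailed output. Tables 14.3.1.2.1 to 14.3.1.3.7.2 (by class, by SOC and PT, by intensity) all come in a Period 1 and a Period 2 version. Only Table 14.3.1.1 and the listings are unsplit.

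**The concern.** The two period rules should together cover every event that the general definition calls treatment-emergent. They do not, because worsening is dropped from the second. It is hard to read worsening into the bare verb in Period 2 when the line above it names occurring and worsening separately.

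Two consequences follow. An event can be treatment-emergent overall and yet have no period. And an event can carry into the on-treatment tables a grade that it reached only after Day 56. The primary objective is safety, and the split exists to separate what happened during the eight weeks of dosing from what came after, so a rule that blurs this should be corrected. No rule in either document says where a worsening after Day 56 goes, so the tables depend on the programmer's reading.

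**Working it through.** **The plan's nearest figure.** The point rests on no stated number. The closest is the 86% power for the primary safety endpoint (SAP 3.5, protocol 9.4): rates of 10% and 50%, 10 placebo and 20 ABX464 subjects, one-sided 10%.

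- Pooled rate = (10 × 0.1 + 20 × 0.5)/30 = 0.367.
- Null standard error = √[0.367 × 0.633 × (1/10 + 1/20)] = 0.187.
- Alternative standard error = √(0.09/10 + 0.25/20) = 0.147.
- Power = Φ[(0.4 − 1.2816 × 0.187)/0.147] = 86.4%.

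The stated figure is reproduced. It concerns the rate in Table 14.3.1.1, which is not split by period, so nothing below changes it.

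**The rules as written.** Let *o* be the onset day and *w* the day of worsening, with first dose on Day 0.

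- Treatment-emergent: *o* ≥ 0 or *w* ≥ 0.
- Period 1: *o* or *w* lies in 0 to 56.
- Period 2 as written: *o* > 56.
- Period 2 with worsening added: *o* > 56 or *w* > 56.
- Grade shown: the maximum over the whole event (SAP 10.1).

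Five illustrative records, each going from grade 1 to grade 3 under one AE number:

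| Record | Treatment-emergent | Period 1 (grade) | Period 2 as written | Period 2 amended |
|---|---|---|---|---|
| 1. Onset before dose, worsens Day 60 | Yes | No | No | Yes |
| 2. Onset Day 20, worsens Day 60 | Yes | Yes (3) | No | Yes |
| 3. Onset Day 60, worsens Day 62 | Yes | No | Yes | Yes |
| 4. Onset before dose, worsens Day 20 | Yes | Yes (3) | No | No |
| 5. Onset Day 20, worsens Day 30 | Yes | Yes (3) | No | No |

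Record 1 has no period. Record 2 sits in Period 1 at a grade first reached on Day 60. Records 3 to 5 are handled correctly.

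**Event counts.** As written, Period 1 holds 3 events (records 2, 4, 5) and Period 2 holds 1 (record 3). That sums to 4, against 5 treatment-emergent events overall. With Period 2 amended, Period 1 holds 3 and Period 2 holds 3 (records 1, 2, 3). That sums to 6, because record 2 is in both.

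**Grade.** Adding worsening to Period 2 does not by itself correct record 2, because the collapse in SAP 10.1 still puts grade 3 in Period 1. Only a maximum taken within each period gives grade 1 in Period 1 and grade 3 in Period 2.

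**The case against.** The case against is substantial, and most of it limits how far the point reaches.

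- **Record 1 is narrow.** A condition present before dosing is normally medical history (SAP 11.2.2). Protocol 8.1 counts an exacerbated disease as an adverse event, and protocol 8.3.1 has abnormal findings present at consent reported if they significantly worsen. An exacerbation on Day 60 recorded with that onset date already falls in Period 2. A true loss needs a pre-dose adverse event record that worsens after Day 56. The introduction to protocol section 8 limits screening events to those related to screening procedures; protocol 8.4 records all events from consent, so such a record is possible. This stands.
- **Record 2 depends on site practice.** If the worsening is entered as a new event with its own start date, it goes to Period 2 as written. Protocol 8.5 asks for a new record when an event recurs and is silent on worsening. This stands.
- **Assigning an event by onset at its maximum grade is a known convention.** True, and it is conservative for Period 1. Nor is Day 60 clearly free of drug: it is 4 × 24 = 96 h after Day 56, about one half-life of the metabolite (90 to 110 h, protocol 5.3.10). But the plan does not state the convention for events that cross Day 56, and its general definition points the other way.
- **Correcting it makes the periods overlap.** Also true; it has to be explained in a footnote.

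A reader might infer more than the documents support:

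- *That late worsening vanishes from all severity output.* It does not. Table 14.3.1.1 has unsplit rows for severe and serious events, and separately reported changes of grade remain in the listings.
- *That the share of follow-up time after Day 56 measures the problem.* For a subject who does not roll over this would be 7/63 = 11% to Day 63, or 28/84 = 33% with the four-week collection in protocol 8.4. These are shares of days under an assumed constant rate. They ignore that the event must have begun by Day 56 and still be open, and that worsening of a later-onset event is already in Period 2. They estimate no table entry.

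**Conclusion.** The rule is wrong as written, in both documents, and the effect is small. A treatment-emergent event can belong to neither period, and an event that becomes severe after Day 56 can be tabulated as severe in Period 1. The second outcome is the likelier of the two.

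The damage is confined to the period-split descriptive tables. The primary comparison, all of Table 14.3.1.1 and the listings are unaffected. With 30 subjects, few events should be involved. How many cannot be derived, because the documents give no rate of worsening, no rollover proportion and no eCRF layout.

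The conclusion assumes that Period 2 is programmed literally. For record 2 it also assumes that the worsening is kept under the original AE number.

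**What to change.** 1. In SAP 11.4.1 and protocol 9.3, add *or worsens* to Period 2, so that both periods use the same test as the treatment-emergent definition.
2. Where the eCRF dates changes of severity, take the maximum grade within each period. Amend the count-once rule in SAP 11.4.1 and the collapse in SAP 10.1 so that they apply within period for the period-split tables. Add a footnote that an event worsening across Day 56 appears in both.
3. Where changes are not dated, keep assignment by onset and say so in the footnote.

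The first step is one phrase in each document. The second is a programming rule, and it is feasible only if the data allow it: protocol 8.5 lists a start date, a stop date and a severity for each event, the count-once rule in SAP 11.4.1 is itself conditional on severity changes being collected, and the shell for Listing 16.2.7 has no date for a change of grade. The eCRF therefore has to be checked first. The price is that event counts for the two periods may sum to more than the overall count, which the footnote should state. No clinical procedure changes.
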